#### **Procedures defining the consent, randomization, post-treatment and 6 month follow-up Veteran assessments:**

All participants will complete assessment interviews at the time of consent, randomization post-intervention (3 month post-randomization), and 3 months post treatment (6 months from randomization). Trained RAs blind to the participant's condition assignment will administer all assessments. In order to ensure that the assessors remain blind, the RA completing the randomization interview (who then informs the participant of their treatment condition) will not complete the post-treatment or 3-month post-treatment follow-up interview with that same participant. However, the post-treatment and 3-month post-treatment follow-up interview may be completed by the same RA. Prior to starting the post-treatment and 3-month post-treatment follow-up, participants will be told not to reveal their study condition (Living Well or medical illness education and support group). If they do, the RA will make a note in the interview materials indicating that the blind was compromised and at what point during the interview this occurred. This RA will still complete the rest of the interview with the participant. If the blind does become compromised, a different RA will conduct the next scheduled assessment. Interviews will take approximately 1 ½ to 2 hours to complete. Please see Detailed Description of Measures section of this protocol for list of assessments and interviews included in the follow-ups.

If study staff is unable to contact enrolled participants by telephone to schedule a randomization, post-intervention, or 3 month post-treatment interview, a letter will be sent to participants to let them know we are attempting to contact them.

Also, we will include CPRS/Chart Summaries of Medical ER Use and Prescribed Medications: CPRS extracted chart data (including admission and discharge codes) will be extracted and used to summarize rates, patterns and reason for visit for the six month interval post randomization. The decision to look at this for a full six months in lieu of immediately post-treatment was made in order to allow for a more realistic timeframe for assessing intervention effects on service utilization. We will also extract details regarding both psychiatric and somatic medications.

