### **Detailed Description of Measures**

#### **Measures/Instruments included in the assessment battery**

1. **The Medical Outcomes Study (MOS) SF-12**: The SF-12 (39), a widely used standardized instrument with strong psychometric properties, will be used to assess self-perceptions of general health functioning across multiple dimensions (including general, physical and emotional/psychiatric functioning). The SF-12 has shown good internal, consistency, stability, and concurrent validity in outpatients with serious mental illness. (instrument is attached to this protocol).

2. Illness Management Self-Efficacy: This questionnaire is based on the items used in the original Chronic Disease Self-Management Program (CDSMP) as part of that group's extensive evaluation of the curriculum (41). The original CDSMP measure has been shown to have strong test-retest reliability and internal consistency as well (41).

3. Patient Activation Measure: This 13-item questionnaire measures an individual's perceived ability to manage his or her illness and health behaviors and act as an effective patient. The measure has demonstrated reliability and validity (36).

4. Measure of Self-Management Behaviors: This questionnaire is based on the items used in the original CDSMP as part of that group's extensive evaluation of the curriculum (41). The original CDSMP measure has been shown to have adequate psychometric properties; the range of test-retest coefficients for the original illness management scales was .56 to .92, with internal-consistency coefficients ranging from .70 to .75.

5 Morisky Medication Adherence Scale: This 8 item self-reported medication adherence scale was developed from a well validated 4-item scale and supplemented with additional items to better capture barriers surrounding adherence behavior. This new scale has demonstrated psychometric properties (43).

6. Basis 24 – Modified: The Basis 24 – Modified is a self-report measure that asks participants about their symptoms and functioning within the time period of a week. Response sets range from “no difficulty – extreme difficulty”, “none of the time – all of the time”, and “never – always”, each with 5 options.

7. Service Utilization and Resources Form (SURF): The SURF has been used successfully in several VA studies to assess service utilization relating to a range of medical services including ER, inpatient and outpatient services (40).

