For proportion with ER use in the past 6 months, we will use a random intercept mixed effects model since this outcome is assessed at only 2 time points. We will use a model that assumes no difference at randomization given the large sample size and randomization to study condition. Thus we will not include study condition as a main effect which would correspond to an assumption of unequal randomization rate of ER use. Some chance variation is expected and we will test the assumption of equal randomization rates with a chi-square test comparing the ER use rates by study condition. This model is equivalent to adjusting for randomization in the continuous case and we are taking this approach to be able to have .80 power to detect a smaller percentage point difference in ER use (50) at the 3 month follow-up assessment than if we didn’t assume equal rates at randomization. In the very unlikely scenario of a statistical difference at randomization we will add the study condition main effect to the model below, and the test of the null for H2 will continue to be the test that the coefficient for the study-condition-by-time interaction term is zero. To compare the two conditions on probability (p) of an ER visit, we let the outcome variable  $Y = 1$  if the participant had an ER visit in the prior 6 months (at randomization or at 3-month follow-up) and  $Y = 0$  if participant did not have an ER visit. Analysis model (logistic mixed effects model, random intercept not displayed) will be:

$$\text{logit}(E[Y]) = \text{Intercept} + \text{site} + \text{covariates} + \text{time} + \text{study-condition} \cdot \text{time}$$

where  $E[Y] = p = \text{probability participant has an ER visit in the prior six months at either randomization or 3 month follow-up (depending on “time” variable)}$ .

Notes: (1) Test of H2 will be the F-test that the coefficient for the study condition-by-time interaction is zero; (2) Study condition indicator main effect is omitted based on assumption of equal rates at randomization as discussed above; (3) For this hypothesis, “time” is a binary variable indicating assessment at 3 months post-treatment versus assessment at randomization; (4) The “covariates” terms represent adjustment for age, race, gender, Charlson comorbidity index score, chronic somatic illness category and other potential confounders found to be significantly different at randomization, (5) We have included a “site” term to adjust for site differences.

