Two, we will examine potential covariate moderators of treatment effect (e.g. participant demographic and clinical characteristics-see list of measures above) on the effectiveness of the intervention. To do this we will utilize the primary models but add the 3-way interaction term between the participant characteristic of interest, study condition indicator and time and through a contrast, test the null hypothesis of no relationship between the covariate and improvement on study outcomes. Three, we will examine effects on additional medical services utilization outcomes (e.g. somatic inpatient hospitalization, outpatient visits) as well as on medication adherence. Models parallel to H2 (ER use) will be used to examine treatment effects on these secondary outcomes. Four, we will examine whether treatment effects differed by site. For these analyses we will include the 3-way interaction term between study condition, time, and site to test overall interaction with an omnibus F-test. If the F-test is significant we will report treatment effects by site, and assess site differences in participant characteristics and otherwise investigate and summarize site characteristics that might explain differences. Five, we will examine how “dose” of intervention (i.e. number of sessions attended) and participation ratings (measured using the Group Performance measure described in the measures section) relate to study outcomes. Separately, in both the Living Well and the control condition we will use regression models to examine whether the covariate (either number of sessions attended or the Group Performance measure) is associated with improvement on outcomes. Models for these analyses (whether outcome is assessed at all 3 time points or just at randomization and 3 mo f/u) will include time and the dose-by-time interaction term to assess the relationship between dose and trajectory over time. For ER use and other dichotomous service utilization outcomes this analysis will assess change in proportion with ER in relation to dose. Six, we will similarly examine how fidelity ratings of adherence and competence relate to the functional, attitudinal, behavioral, and service related outcomes specified. In models similar to those used above to examine dose response relationships we will examine the relationship between overall adherence (and competence) and change in outcomes separately for each condition.

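### Medication adherence, an interview scale measured at three trial assessments, is placed under the two-time-point binary model built for ER use; the model used for the other interview scales fits it better

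*Protocol*

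**What the plan says.** Item Three of the exploratory analyses (Protocol, Data Analysis) looks at effects on "additional medical services utilization outcomes (e.g. somatic inpatient hospitalization, outpatient visits) as well as on medication adherence", and then states: "Models parallel to H2 (ER use) will be used to examine treatment effects on these secondary outcomes".

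The model for Hypothesis 2 is set out earlier in the same section. Its structure is justified by the outcome: "we will use a random intercept mixed effects model since this outcome is assessed at only 2 time points". The form is explicit: "Analysis model (logistic mixed effects model, random intercept not displayed) will be" an equation for the logit of the probability of an ER visit in the prior six months. Time in that model "is a binary variable indicating assessment at 3 months post-treatment versus assessment at randomization", so it has no post-treatment level.

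The adherence measure is item 5 under Detailed Description of Measures: "This 8 item self-reported medication adherence scale was developed from a well validated 4-item scale". It is listed in the battery in the Assessment/Interview Study Schedule, which is marked for all four interviews. The procedures section agrees: "All participants will complete assessment interviews at the time of consent, randomization post-intervention (3 month post-randomization), and 3 months post treatment".

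For the other interview scales the plan differs. Under Hypotheses 3 and 4, self-efficacy, patient activation and self-management behaviors are assigned models parallel to Hypothesis 1. That is a longitudinal mixed model with time coded 0, 3 and 6 months.

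**The concern.** Adherence is an interview scale, but it has been grouped with the chart-based service-use outcomes. Two features of the H2 model suit ER use and do not suit adherence.

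- **Binary outcome.** A six-month event is naturally yes or no. An 8-item score is not, and the protocol gives no cut-point. Cutting a score loses information, and an unstated cut could be chosen after the data are seen.
- **Two time points.** Adherence is also measured at post-treatment. Followed as written, the model leaves that assessment out although it will have been collected.

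At stake is the precision of one exploratory comparison, and its consistency with the analysis of similar scales in the same trial.

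**Working it through.** **1. The plan's own figure for the H2 comparison.** Inputs from Sample Size: 10.7% versus 25%, two-sided alpha .05, power .80. The difference is d = 0.143 and the mean proportion is 0.1785.

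n per arm = [1.96·√(2·0.1785·0.8215) + 0.8416·√(0.107·0.893 + 0.25·0.75)]² / 0.143² = 111.4, so 112.

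With the continuity correction: (111.4/4)·[1 + √(1 + 4/(111.4·0.143))]² ≈ 125.

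The stated 125 per condition is reproduced with the correction. It concerns ER use and is not touched by this point. No power figure is stated for adherence.

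**2. Does the H2 form fit adherence?**

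| Feature | ER use (H2) | Medication adherence | Other interview scales (H3, H4) |
|---|---|---|---|
| Source | Chart | Interview | Interview |
| Outcome | Yes/no over six months | 8-item score | Scale scores |
| Time points for a trial comparison | 2 | 3 (plus consent) | 3 (plus consent) |
| Model assigned | Logistic, binary time | Parallel to H2 | Parallel to H1 |

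Adherence matches the last column in every row except the model.

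**3. Illustration of what a cut costs.** The Sample Size section supplies 0.40 SD and 110 per arm after 12% loss. Both are planning values for the SF-12, borrowed here. The normal score and the cut-points are assumptions.

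Continuous score, one follow-up: standard error = √(2/110) = 0.1348. Power = Φ(0.40/0.1348 − 1.96) = Φ(1.01) = 0.84. This is a single-time comparison, not a check of the protocol's .89 for the repeated-measures SF-12 analysis.

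Cut score: if a share q of one arm lies above the cut c, the share in the other arm is 1 − Φ(c − 0.40). Power comes from the two-proportion z-test without continuity correction. The information kept is φ(c)²/[q(1 − q)].

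| q above cut | Share in other arm | Information kept | Power |
|---|---|---|---|
| 50% (median) | 65.5% | 64% | 0.65 |
| 30% | 45.0% | 58% | 0.64 |
| 20% | 32.9% | 49% | 0.59 |
| 10% | 18.9% | 34% | 0.47 |

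For the median cut, the difference is 0.155, the null standard error 0.0666 and the alternative standard error 0.0658. Power is Φ[(0.155 − 1.96·0.0666)/0.0658] = Φ(0.38) = 0.65.

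**4. Outpatient visits as any versus none.** The documents give no visit rate, so a range is assumed, with 125 per arm and the same z-test.

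| Assumed rate in one arm | Other arm must fall to (80% power) | Power if other arm reached 100% |
|---|---|---|
| 80% | 64% | about 1.00 |
| 90% | 77% | 0.96 |
| 95% | 84% | 0.72 |
| 98% | 89% | 0.36 |

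How much a binary comparison can show depends entirely on a rate the protocol does not state.

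**The case against.** The strongest reply is that the protocol speaks of models parallel to H2, in the plural, not of the H2 model itself. The H2 text draws a comparison with the continuous case, so its authors may have had a continuous analogue in mind. The only sentence in the exploratory list that calls outcomes dichotomous concerns service use. Nothing says that the adherence scale will be cut, and the scoring of an exploratory outcome may well be settled in an analysis plan not seen here. This stands to the extent that a reader should not conclude the protocol forces dichotomization: it implies it as worded. But no other link or time coding is named for adherence. Even with a continuous outcome, a model that keeps H2's binary time still omits the post-treatment score.

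Three stronger readings are tempting but not supported:

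- **That the outpatient analysis is close to uninformative because nearly everyone has a visit.** Participants must receive mental health services and have a charted chronic condition, but the outcome is visits to medical providers, and no rate is given. Any versus none is a legitimate, if coarser, question. The two six-month windows suit service use, so no post-treatment value is lost there.
- **That the lost assessment is the one at which the intervention acts most.** Living Well continues with monthly boosters for three months after the weekly groups, so a test at the 3-month follow-up is also reasonable.
- **That the cost analysis is affected.** It is specified separately, from VA administrative and chart data and the SURF, and nothing says that it draws on these models.

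**Conclusion.** The point holds for medication adherence. The plan assigns a repeatedly measured interview scale to a model whose stated rationale does not apply to it, which departs from its own handling of comparable scales. Read as written, this leaves out one of three available assessments and implies a cut that is not given.

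The drop from 0.84 to between 0.65 and 0.47 shows the possible cost of a cut. It does not measure an error in a stated figure, since the effect size, normality and cut-points are all assumed.

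For outpatient visits only a mild remark remains: any versus none cannot show a change in the number of visits. The matter is minor, because these analyses are exploratory. Hypotheses 1 to 5 and N=250 are unaffected.

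**What to change.** In item Three of the exploratory analyses, state that medication adherence is analysed as a scale score with the longitudinal mixed model parallel to Hypothesis 1, using randomization, post-treatment and 3-month follow-up. Keep the H2-parallel logistic models for dichotomous six-month service-use outcomes, such as any somatic hospitalization. If a binary adherence result is also wanted, fix its cut-point before the data are examined.

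Optionally, also report outpatient visits as counts over the same six-month windows, for example with a negative binomial mixed model.

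The cost is one sentence and standard model code. The scale is already scheduled and the visit data are already to be collected.

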#### FOR PROCESS EVALUATION:

Our PROCESS EVALUATION relies on the RE-AIM evaluation framework to better understand contextual factors that support the conduct of the proposed trial and that will affect future efforts to implement and sustain the Living Well intervention in the VA system of care. The proposed evaluation also provides a distinct and complementary avenue for understanding differential outcomes across conditions. This evaluation will integrate findings from two streams of inquiry: 1) A qualitative study that combines focus groups and in-depth individual interviews conducted both before and after the clinical trial, and; 2) a cost analysis focused on implementation/operating costs and cost consequences. Data from both, in combination with outcome data generated by the trial, will be synthesized and applied to the RE-AIM framework foci (see table below) and used to help draft an implementation toolkit detailing procedures, resources and considerations needed to successfully deliver Living Well in VA mental health settings.

**Pre-Trial Focus:** Prior to initiating the effectiveness trial, we will conduct a series of qualitative focus groups and/or individual interviews with a range of key stakeholders to: 1) Identify obstacles and barriers that might impede the proposed trial, and; 2) collect contextual information that will inform future dissemination and sustainability of the Living Well intervention in the broader VA context.

**Post-Trial Focus:** After completing the effectiveness trial (AIM 1) we will conduct both focus groups and in-depth individual interviews with Veteran study participants, Veterans who served as peer co-facilitators in the Living Well condition, and various stakeholders involved in the pre-trail evaluation to:

1) extend and enhance our understanding of intervention outcome and processes, and; 2) inform the development of an implementation toolkit to support future dissemination efforts.

### **Potential Risks/Discomforts**

#### **Risks associated with the EFFECTIVENESS TRIAL (and for each, provisions for minimizing risk):**

##### **1. Breach of confidentiality of research data:**

There is a slight risk of a confidentiality breach related to data collected for research purposes from participant interviews and medical records. Study participants will be informed that information obtained through research interviews is confidential; potential risks to data security and the measures we take to protect it will be reviewed with them during the informed consent process. Numerous steps will be taken to ensure research interview data confidentiality and security. To protect confidentiality, coded hard copies of interview assessment data and data obtained from participants' medical records are kept in a locked file cabinet behind a locked office door. All hard copies of research assessment forms will be stored in a locked cabinet in a locked office in the University of Maryland, Division of Services Research. Only designated research staff has access to the password protected file that links participants' identities to their codes. This file is located on a secure server located in the VA Maryland Health Care System.

Consent forms which contain participants' names are kept in a locked cabinet in a locked office that is located in the VA Maryland Health Care System.

Electronic data are kept on a password protected computer server, of which the passwords are only known to the study team members. Electronic research data are backed up regularly. All electronic research data with identifiers will be stored behind the VA firewall.

In the event of any incidents, unauthorized access of sensitive data or storage devices or noncompliance with security controls, the PI or another member of the research staff will immediately contact the VAMHCS Information Security Officer, Privacy Officer and the VAMHCS Research Compliance Officer.

##### **2. Distress During Assessments:**

Before consent and before and during each data collection, participants are informed that they are free to decline to answer any interview question(s) or to discontinue the interview at any time. If participants feel uncomfortable or fatigued, or seem so to the RA, they are encouraged to take a break and continue again later, or to stop the interview. In our research with people with serious mental illnesses over the past several years, few research participants have expressed discomfort from participating in the interviews. Nonetheless, all RAs have been trained to stop the interview if a participant becomes distressed and will have the resources needed to assist him/her in obtaining the level of support or assistance they require, including crisis intervention if needed.

##### **3. Distress During Groups:**

Participants may feel self-conscious sharing their beliefs/thoughts while in groups. We will minimize this by reminding participants that they can choose to not answer questions if they feel uncomfortable. We will also remind participants that what is said in group should remain confidential and not be shared with anyone outside of group.

4. Participants may experience some discomfort in being recorded during study interviews and group meetings:

Participants will be told that the digital recorder may be turned off at any time during the group meeting or interview if this occurs. There is also a slight risk of a breach of confidentiality regarding the identities of the participant on the recording. To minimize this risk, research staff will label all digital recordings with a code. Access to the file that links participant names to their project ID number will be stored behind the VA firewall.

**Risks associated with the PROCESS EVALUATION (and for each, provisions for minimizing risk):**

1. Breach of confidentiality of research data:

There is a slight risk of a confidentiality breach related to data collected for research purposes from participant interviews and focus groups. Study participants will be informed that information obtained through research interviews is confidential; potential risks to data security and the measures we take to protect it will be reviewed with them during the informed consent process. Numerous steps will be taken to ensure research interview data confidentiality and security. To protect confidentiality, all digitally recorded interviews and focus groups are coded and are kept in a locked file cabinet behind a locked office door. Only designated research staff has access to the password protected file that links participants' identities to their codes. This file is located on a secure server located in the VA Maryland Health Care System.

2. Distress During Focus Groups:

Participants may feel self-conscious sharing their beliefs/thoughts while in focus groups or during interviews. We will minimize this by reminding participants that they can choose to not answer questions if they feel uncomfortable. We will also remind participants that what is said in the focus groups should remain confidential and not be shared with anyone outside of the focus group.

3. Participants may experience some discomfort in being recorded during interviews and focus groups:

Participants will be told that the digital audio recorder may be turned off at any time during the focus group or interview if this occurs. There is also a slight risk of a breach of confidentiality regarding the identities of the participant on the recording. To minimize this risk, research staff will label all digital recordings with a code number. Access to the file that links participant names to their project ID number will be stored behind the VA firewall.

